#### 11.1.1. Adverse Event (AE)

An AE is any untoward medical occurrence, unintended disease or injury, or untoward clinical signs (including abnormal laboratory findings) in subjects, users or other persons, whether or not related to the investigational medical device.\*

\*For the purposes of this clinical study, AE definitions will be ISO 14155:2011 compliant with the following exception: only those AEs that are related to the Emprint™ Ablation Catheter Kit with Thermosphere™ Technology, accessory devices, or study procedures will be captured and reported.

- NOTE 1: This definition includes events related to the investigational medical device or the comparator.
- NOTE 2: This definition includes events related to the procedures involved.

NOTE 3: For users or other persons, this definition is restricted to events related to investigational medical devices.

#### 11.1.2. Serious Adverse Event (SAE)

For the purposes of this study, a Serious Adverse Event (SAE)\* is an AE that has

- 1. Led to death,
- 2. Led to serious deterioration in the health of the subject, that either resulted in
  - a. A life-threatening illness or injury, or
  - b. A permanent impairment of a body structure or a body function, or
  - c. In-patient or prolonged hospitalization, or
  - d. Medical or surgical intervention to prevent life-threatening illness or injury or permanent impairment to a body structure or a body function.

MDT18010ILSBA

Version 4.0

26-SEP-2019

Page 34 of 50

3. Led to foetal distress, foetal death or a congenital abnormality or birth defect

NOTE 1: This includes device deficiencies that might have led to an SAE if a) suitable action had not been taken or b) intervention had not been made or c) if circumstances had been less fortunate. These are handled under the SAE reporting system.

NOTE 2: Planned hospitalization for a pre-existing condition, or a procedure required by the clinical investigational plan, without serious deterioration in health, is not considered an SAE.

\*For the purposes of this clinical study, SAE definitions will be ISO 14155:2011 compliant with the following exception: only those SAEs that are related to the Emprint™ Ablation Catheter Kit with Thermosphere™ Technology, accessory devices, or study procedures will be captured and reported.

#### 11.1.3. Adverse Device Effect (ADE)

An Adverse Device Effect (ADE) is an AE related to the use of the investigational medical device (the Emprint™ Ablation Catheter Kit with Thermosphere™ Technology).

NOTE 1: This definition includes AEs resulting from insufficient or inadequate instructions for use, deployment, implantation, installation, or operation, or any malfunction of the investigational medical device.

NOTE 2: This definition includes any event resulting from use error or from intentional misuse of the investigational medical device.

#### 11.1.4. Serious Adverse Device Effect (SADE)

A Serious Adverse Device Effect (SADE) is an adverse device effect that has resulted in any of the consequences characteristic of an SAE.

### 11.1.5. Unanticipated Serious Adverse Device Effect (USADE)

An Unanticipated Serious Adverse Device Effect (USADE) is defined as serious adverse device effect which by its nature, incidence, severity or outcome has not been identified in the current version of the Risk Management Report.

NOTE: Anticipated serious adverse device effect (ASADE) is an effect which by its nature, incidence, severity or outcome has been identified in the risk analysis report.

#### 11.1.6. Device Deficiency

Inadequacy of a medical device with respect to its identity, quality, durability, reliability, safety or performance.

Note: Device deficiencies include malfunctions, use errors, and inadequate labelling.

MDT18010ILSBA

Version 4.0

26-SEP-2019

Page 35 of 50

#### 11.1.7. Adverse Event Relationship Classification

Causality assessments define the relationship between the use of the medical device (including the procedure) and the occurrence of each AE. During causality assessment activity, clinical judgment shall be used and the relevant documents, such as the MDR Reportable Event Trend & Risk Analysis Report shall be consulted, as all the foreseeable SAEs and the potential risks are listed and assessed there. The presence of confounding factors, such as concomitant medication/treatment, the natural history of the underlying disease, other concurrent illness or risk factors shall also be considered.

Each AE and SAE will be classified according to five different levels of causality. The following definitions will be used to assess the relationship of the AE to the investigational medical device (the Emprint™ Ablation Catheter Kit with Thermosphere™ Technology), accessory devices, or study procedures:

- Not related: Relationship to the device or procedures can be excluded when:
- the event is not a known side effect of the product category the device belongs to or of similar devices and procedures
- the event has no temporal relationship with the use of the investigational device or the procedures;
- the serious event does not follow a known response pattern to the medical device (if the response pattern is previously known) and is biologically implausible;
- the discontinuation of medical device application or the reduction of the level of activation/exposure - when clinically feasible – and reintroduction of its use (or increase of the level of activation/exposure), do not impact on the serious event;
- the event involves a body-site or an organ not expected to be affected by the device or procedure;
- the serious event can be attributed to another cause (e.g. an underlying or concurrent illness/ clinical condition, an effect of another device, drug, treatment or other risk factors);
- the event does not depend on a false result given by the investigational device used for diagnosis, when applicable;
- harms to the subject are not clearly due to use error;
- o In order to establish the non-relatedness, not all the criteria listed above might be met at the same time, depending on the type of device/procedures and the serious event.
  - *Unlikely*: The relationship with the use of the device seems not relevant and/or the event can be reasonably explained by another cause, but additional information may be obtained.
  - Possible: The relationship with the use of the investigational device is weak but cannot be ruled out completely. Alternative causes are also possible (e.g. an underlying or concurrent illness/clinical condition or/and an effect of another device, drug or treatment). Cases were relatedness cannot be assessed or no information has been obtained should also be classified as possible.
  - *Probable*: The relationship with the use of the investigational device seems relevant and/or the event cannot reasonably be explained by another cause, but additional information may be obtained.

MDT18010ILSBA Version 4.0 26-SEP-2019 Page 36 of 50

Medtronic

- *Causal relationship*: The serious event is associated with the investigational device or with procedures beyond reasonable doubt when:
- the event is a known side effect of the product category the device belongs to or of similar devices and procedures;
- the event has a temporal relationship with investigational device use/application or procedures;
- o the event involves a body-site or organ that
- the investigational device or procedures are applied to;
- o the investigational device or procedures have an effect on;
- the serious event follows a known response pattern to the medical device (if the response pattern is previously known);
- the discontinuation of medical device application (or reduction of the level of activation/exposure) and reintroduction of its use (or increase of the level of activation/exposure), impact on the serious event (when clinically feasible);
- o ther possible causes (e.g. an underlying or concurrent illness/ clinical condition or/and an effect of another device, drug or treatment) have been adequately ruled out;
- o harm to the subject is due to error in use;
- the event depends on a false result given by the investigational device used for diagnosis, when applicable;
- In order to establish the relatedness, not all the criteria listed above might be met at the same time, depending on the type of device/procedures and the serious event.

Events will be distinguished between the SAEs related to the device and those related to the procedures (any procedure specific to the clinical investigation). An AE can be related both to procedures and the device. Complications of procedures are considered not related if the said procedures would have been applied to the patients also in the absence of device use/application.

In some particular cases the event may be not adequately assessed because information is insufficient or contradictory and/or the data cannot be verified or supplemented. The sponsor's Medical Monitor and the Investigators will make the maximum effort to define and categorize the event and avoid these situations. Where the Medical Monitor remains uncertain about classifying the serious event, it should not exclude the relatedness and classify the event as "possible".

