MDT18010ILSBA

Version 4.0

26-SEP-2019

Page 17 of 50

1 major complication occurred: pneumothorax. Minor complications included self-resolving pneumothorax (14 of 28 sessions) and perilesional hemorrhagic effusion (13 of 28 sessions), as well as hospitalization-related lower urinary tract infection in 3 of 28 sessions. An additional unpublished sponsored study (NCT02323854) also describes use of the Emprint™ Ablation System in the lung using a percutaneous approach in 15 subjects. All 15 subjects underwent ablation followed by planned surgical resection. Complete ablation was detected in 54.4% (6/11), incomplete ablation in 36.4% (4/11), and delayed necrosis in 9.1% (1/11). There were no device-related AEs reported. A total of 5 SAEs occurred in 3 subjects (20%). SAEs included acute respiratory failure, pulmonary air leakage, prolonged air leak, Guillain-Barre Syndrome, and respiratory arrest, which resolved after the procedure. All 5 SAEs were either not related or unlikely to be related to the procedure. Twelve AEs were related to the ablation procedure, including bleeding, pneumothorax (Grade 1, n=4), hemoptysis (Grade 1, n=1), hemothorax (Grade 2, n=2), and vasovagal syncope (Grade 1, n=1). These studies demonstrate that the Emprint™ Ablation System performed as expected with a safety profile consistent with the known safety profile for lung ablation.

The Emprint™ Ablation Catheter was introduced as part of the Emprint™ Ablation System in 2016. Its CE mark was based on equivalence to the percutaneous antenna utilizing the same Thermosphere™ technology. Therefore, the proposed clinical study will be conducted specifically to characterize the safety and performance of the catheter device in the lung with a bronchoscopic approach.

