#### 11. Adverse Events and Device Deficiencies

# 11.1. Definitions/Classifications

Adverse event (AE) definitions used in this study are based on ISO 14155:2011 (Clinical Investigation of Medical Devices for Human Subjects -- Good Clinical Practice;

https://www.iso.org/obp/ui/#iso:std:iso:14155:ed-2:v1:en), which is aligned with MEDDEV 2.7/3

MDT18010ILSBA

Version 4.0

26-SEP-2019

Page 33 of 50

Revision 3, May 2015 (Guidelines on Medical Devices, Clinical Investigations: Serious Adverse Event Reporting).

For the purpose of this clinical study investigational plan, the point of enrollment is defined as the insertion of the Emprint™ Ablation Catheter Kit with Thermosphere™ Technology into the EWC. AEs will be collected beginning at the point of enrollment. For safety reporting, only AEs related to the procedure or study devices will be captured and reported until the subject exits the study. Any unresolved procedural or device related events that are still ongoing past study exit will be monitored by the physician per their institutional standard-of-care.

Anticipated AEs are listed in Section 10.1.

AEs related to the Emprint™ Ablation Catheter Kit with Thermosphere™ Technology, accessory devices, or study procedures will be adjudicated by an independent medical monitor.

Refer to the NAVABLATE Adverse Event Reference List (Appendix 17.5) for additional definitions.

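### Being new to the device class is an unqualified ground for grading an event Not related, and because only related events are captured, a new effect could be left out of the data

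*Protocol*

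**What the plan says.** **Grading.** Section 11.1.7 of the protocol sets five causality levels. Under *Not related* it lists grounds on which a relationship can be excluded. The first is that "the event is not a known side effect of the product category the device belongs to or of similar devices and procedures". The list closes with "In order to establish the non-relatedness, not all the criteria listed above might be met at the same time". It gives no minimum number of grounds and no required combination. Appendix 17.5 (the Adverse Event Reference List) repeats the same text.

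**Capture.** Section 11.1 says that "only AEs related to the procedure or study devices will be captured and reported until the subject exits the study". Section 11.1.1 declares an exception to ISO 14155, under which "only those AEs that are related to the Emprint™ Ablation Catheter Kit" (or to accessories or study procedures) are captured. Section 11.1.2 makes the same exception for serious events: "only those SAEs that are related to the" device, accessories or procedures. Section 14.1 restates the exception, and Section 11.2.1 limits reportable AEs and SAEs in the same way.

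**Review.** In Section 11.1, adjudication is stated for events related to the catheter kit, "accessory devices, or study procedures will be adjudicated by an independent medical monitor". Section 12 says there is no Clinical Events Committee.

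**Counting.** SAP 7.8.1.5 treats *Unlikely*, *Possible* and *Probable* all as related. Only *Not related* falls outside.

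**New effects.** Section 11.1.5 defines an unanticipated serious adverse device effect (USADE) as one which by its nature, incidence, severity or outcome "has not been identified in the current version of the Risk Management Report". Section 6.2 explains that the catheter's CE "mark was based on equivalence to the percutaneous antenna", and gives this as the reason for studying the bronchoscopic approach.

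**The concern.** The study exists to characterise the safety of a catheter used by a route for which the protocol cites little direct human evidence. Its prior Emprint data in people come from liver, pancreas and percutaneous lung ablation; the bronchoscopic in vivo study it describes is in six swine (Section 6.2). In that setting, an effect that nobody has described before is one of the things the study should be able to record. Yet being undescribed is itself a listed reason to exclude a relationship.

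If all adverse events were captured, a doubtful grade could be reviewed and corrected later. Under related-only capture, an event graded *Not related* to the catheter, the accessories and the procedure has no stated route to the AE form or to the medical monitor. The primary rate and the three secondary safety rates would then be too low by whatever was left out.

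**Working it through.** There is no figure in the plan to reproduce: the study has no power calculation and no expected primary rate. The check is mainly of the text, with a small calculation for scale.

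**1. Is the novelty ground qualified?** No. A neighbouring ground, departure from a known response pattern, applies only where that pattern is already known and also requires biological implausibility. The novelty ground carries no such condition.

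**2. Is it enough alone?** The text does not say. The closing sentence removes the need to meet every ground but sets no floor. Requiring two grounds would not help much, because two others fit almost any event in a therapeutic study: no dependence on a false diagnostic result, and harm not clearly due to use error.

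**3. Do the default rules catch it?** Section 11.1.7 sends an event to *Possible* when relatedness cannot be assessed, when no information has been obtained, or when the medical monitor remains uncertain about a serious event. None of these applies to a site that confidently invokes a listed ground. The rule in SAP 7.8.1.5 acts only on events that have already been captured.

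**4. Which events are exposed?** Only those absent from the known profile of the product category and of similar devices and procedures. That profile is wide: Section 10.1.1 lists 18 residual risks, Appendix 17.5 defines 20 potential events including pneumothorax and bronchopleural fistula, and Section 4.1 cites a meta-analysis of 15 studies of navigated bronchoscopic access. What remains is events new in nature.

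**5. Scale of one lost subject.** Inputs: N up to 30 (SAP 6), approximate minimum 20 (Protocol Section 3), and a two-sided 95% exact binomial interval for the primary endpoint (SAP 7.7).

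- Shift in the rate = 1/N: 1/30 = 3.3 points; 1/20 = 5.0 points.
- With no events, the upper limit is 1 − 0.025^(1/N): 11.6% at N=30 and 16.8% at N=20.
- With one event, the Clopper-Pearson interval is 0.1% to 17.2% at N=30 and 0.1% to 24.9% at N=20.

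So if the lost subject had the only event, the reported upper limit would be 11.6% instead of 17.2%, or 16.8% instead of 24.9%.

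**6. Chance of recording a new effect at all.** Let p be the true rate of the effect and c the share of such events not screened out. Both are assumptions; the documents give neither. The chance of at least one recorded subject is 1 − (1 − pc)^N.

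| p | c | N=20 | N=30 |
|---|---|---|---|
| 3% | 1 | 45.6% | 59.9% |
| 3% | 0.5 | 26.1% | 36.5% |
| 5% | 1 | 64.2% | 78.5% |
| 5% | 0.5 | 39.7% | 53.2% |
| 10% | 1 | 87.8% | 95.8% |
| 10% | 0.5 | 64.2% | 78.5% |

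At c = 0 the chance is zero throughout.

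**The case against.** The strongest reply is that no single item in the list can have been meant to decide the grade. If any one sufficed, the two near-universal grounds would make almost every event in this study *Not related*. Section 11.1.7 also calls for clinical judgment, consultation of the risk analysis and attention to confounders. An event that begins after catheter insertion with no other explanation would ordinarily fit *Possible* already, since the relationship cannot be ruled out. This stands in part. A reader might infer that novelty alone establishes *Not related*, and the documents do not say that. They leave it open, which is the defect.

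A reader might also infer that the rule screens out USADEs as a class. It does not. A USADE can be unanticipated in incidence, severity or outcome as well as nature, and is judged against the Risk Management Report, whereas the criterion refers to known effects of the category and of similar procedures. The two overlap only for effects new in nature.

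Nor is loss of the record certain. Section 11.1.7 says each AE is graded on five levels, *Not related* among them. SAP 7.2 says adverse events for all enrolled subjects will be collected, and the AE definition in SAP 7.8.1.1 omits the related-only exception. Monitors review subject charts (Section 15.1), and device deficiencies are reported separately (Section 11.2.1). These points sit uneasily with the capture rule but do not override it, and none gives an event called *Not related* a defined path to the medical monitor.

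Finally, the consequence comes from related-only capture, which is a declared choice, so events excluded on other grounds would remain uncaptured. That is true. It limits what this change achieves without removing the reason for making it.

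**Conclusion.** The point holds as a narrow one. An unqualified novelty ground, with no statement of whether it is enough alone, combined with related-only capture and adjudication, allows a site following the text to leave out an event that is new in nature. The primary and secondary safety rates could then be too low.

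It would go too far to say that the rates are biased downward by a known amount. The number of affected events is unknown and may be small, or zero. The 3.3 or 5.0 points is simply 1/N and applies to any missed subject. Counting *Unlikely* as related works in the opposite direction, so a net bias is not established. An event judged unrelated to the catheter but related to the procedure or an accessory is lost to the primary endpoint only; it still reaches the broader secondary endpoints in SAP 7.7.2.

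The conclusion assumes that the protocol's capture rule governs what sites enter. The change is still worth making: it is cheap, and it replaces a stated rule that permits the omission.

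**What to change.** Keep the criterion, but add a qualifier in both Section 11.1.7 and Appendix 17.5. Absence from the known profile cannot by itself establish *Not related*. It may support that grade only together with no temporal relationship or an established other cause. Otherwise the event is graded at least *Possible*, captured and sent to the medical monitor. Give sites a short training note to match.

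Also reconcile SAP 7.2, which says adverse events for all enrolled subjects are collected, with the protocol's related-only capture rule, so that sites and programmers work from the same definition.

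The cost is a one-sentence qualifier in two places, an SAP clarification, a few more AE forms and a possibly slightly higher reported AE rate.

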## 5.1.2. Secondary Objectives

The following secondary endpoints will be evaluated:

- Composite rate of serious AEs (SAEs) related to the Emprint™ Ablation Catheter Kit with Thermosphere™ Technology through 1-month follow-up.
- Composite rate of all AEs related to the procedure or study devices through 1-month follow-up.

MDT18010ILSBA Version 4.0

26-SEP-2019

Page 15 of 50

- Composite rate of all SAEs related to the procedure or study devices through 1-month follow-up.
- Patient satisfaction and pain (Bronchoscopic Ablation Patient Pain and Satisfaction Survey)
- Quality of life evaluation (EQ-5D scale)
- Technical success: An evaluation of whether the lung nodule was treated according to the study
  protocol as determined at the immediate post-procedural timepoint. This is in contrast to
  procedures in which the protocol could not be executed completely, either for technical reasons or
  for reasons related to comorbid disease.
- Technique efficacy: An evaluation of whether the lung nodule was effectively ablated. Evaluates whether complete ablation of the nodule was achieved as evidenced by imaging follow-up 1-month post-procedure (including a window of 20-40 days post-procedure).

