#### 8.3. Inclusion Criteria

- 1. Subject is ≥ 18 years of age
- 2. Subject has provided informed consent
- 3. Subject is able and willing to comply with the study follow-up schedule
- 4. Subject has a definitive diagnosis of cancer in the lung
- 5. Target nodule is ≤ 30mm in maximum diameter
- 6. There is ≥ 5mm of nodule-free lung parenchyma between target nodule and pleura or fissure
- 7. Subject is a candidate for an elective ENB procedure
- 8. Subject is a candidate for an elective lung ablation procedure according to standard of care and product Instructions for Use
- 9. Subject is not a candidate for lung surgery or refuses lung surgery
- 10. Subject is not a candidate for stereotactic body radiation therapy (SBRT) or refuses SBRT

MDT18010ILSBA

Version 4.0

26-SEP-2019

Page 22 of 50

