#### 10.2. Potential Benefits

Benefit estimations of the general use of the Emprint™ Ablation Catheter with Thermosphere™ Technology are described in the Risk Management Report for the Emprint™ Ablation System with the Ablation Catheter.

Microwave ablation is an alternative for patients with lung cancer who are either ineligible for or refuse other treatments such as surgical resection. Furthermore, bronchoscopic ablation may result in fewer complications than percutaneous ablation (see Section 4.1). For patients who are not candidates for alternative therapies, the benefits of microwave ablation outweigh the risks described above.

The bronchoscopic ablation procedure described in this study is commercially available. Patients could receive these potential benefits without taking part in the study and may not gain any direct medical benefits compared to routine care. However, the data collected from this study will help characterize the safety and performance of the Emprint™ Ablation Catheter with Thermosphere™ Technology. If the results of this study support additional clinical research, further studies may be justified to evaluate the potential for improved standard-of-care using microwave ablation technology in lung nodules.

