7.7.2 Secondary Endpoints

The following secondary endpoints will be evaluated:

7.7.2.1 Composite rate of serious adverse events related to the Emprint™ Ablation Catheter Kit with Thermosphere™ Technology through 1-month follow-up.

It is calculated as follows:

- if the question of "Is the AE serious?" is checked "YES" (in the CEC_NC CRF), and
- if the question of "Is the AE related to the Emprint Ablation Catheter?" is checked "YES" (in the CEC_NC CRF), and

7.7.2.2 Composite rate of all adverse events (AEs) related to the procedure or study devices through 1-month follow-up.

It is calculated as follows:

- if at least one of the following questions is checked "YES" (in the CEC_NC CRF)
 - o "Is the AE related to the Emprint Ablation Catheter?", or
 - o "Is the AE related to the ENB procedure?", or
 - o "Is the AE related to the ablation procedure?", or
 - o "Is the AE related to anesthesia for the study procedure?", or
 - o "Is the AE related to the superDimension Navigation System?", or
 - o "Is the AE related to the Positioning Tool?", and

7.7.2.3 Composite rate of all serious adverse events (SAEs) related to the procedure or study devices through 1-month follow-up.

It is calculated as follows:

- if the question of "Is the AE serious?" is checked "YES" (in the CEC_NC CRF), and
- if at least one of the following questions is checked "YES" (in the CEC_NC CRF)
 - o "Is the AE related to the Emprint Ablation Catheter?", or

Form

Medtronic

Revision [1.0]

Page 11 of 15

- "Is the AE related to the ENB procedure?", or
- "Is the AE related to the ablation procedure?", or
- "Is the AE related to anesthesia for the study procedure?", or
- o "Is the AE related to the superDimension Navigation System?", or
- o "Is the AE related to the Positioning Tool?", and

7.7.2.4 Patient satisfaction, pain and level of breathlessness (Bronchoscopic Ablation Patient Pain, level of breathlessness, and Satisfaction Survey)

For each of the question in the PT_SAT CRF, the data will be summarized using frequency measures in the format of p% (x/N) with p and x being the percentage and number of subjects with "YES" answer to evaluation questions and N being the number of all subjects who fill the satisfaction evaluation. Continuous variables (e.g. Pain or discomfort level subjects experienced because of the bronchoscopic ablation procedure) will be summarized with number of subjects (n), mean, standard deviation, median, and ranges.

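### The relatedness wording in Protocol 11.1.7 lets a site leave out procedure complications that two secondary safety endpoints are meant to count

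*Protocol*

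**What the plan says.** **Attribution rule.** Protocol 11.1.7 separates serious events related to the device from "those related to the procedures (any procedure specific to the clinical investigation"). It then adds: "Complications of procedures are considered not related if the said procedures would have been applied to the patients" even without the device. The AE Reference List (Appendix 17.5) repeats both statements.

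**Endpoints.** Protocol 5.1.2 and 9.8.5 include "Composite rate of all AEs related to the procedure or study devices through 1-month follow-up" and a matching endpoint for SAEs. SAP 7.7.2.2 and 7.7.2.3 build them from CRF questions such as "Is the AE related to the ENB procedure", with parallel questions on the catheter, the ablation procedure, anesthesia, the navigation system and the positioning tool. One YES is enough, and the SAEs must also be marked serious. SAP 7.8.1.5 treats *unlikely*, *possible* and *probable* as related and *not related* as unrelated.

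**Capture.** Under Protocol 11.1.1, only AEs related to the catheter kit, "accessory devices, or study procedures will be captured and reported". Section 11.1 says the same and starts AE collection when the catheter enters the extended working channel (EWC).

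**Setting.** Protocol 8.3 requires that "Subject is a candidate for an elective ENB procedure" and, separately, a candidate for standard-of-care lung ablation. Section 10.2 says "The bronchoscopic ablation procedure described in this study is commercially available". Section 10.1.3 calls the CT scan and procedural imaging part of routine care.

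**The concern.** Two limits in 11.1.7 decide which procedure complications count as related. One asks whether the procedure is specific to the investigation; the other asks whether it would have happened without the device. The SAP endpoints contain neither limit, and nothing in either document exempts them.

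In a study that records every AE, this would be a labelling question that could be settled at analysis. Here relatedness also decides capture. An event that a site classes as *not related* need not reach the eCRF, and the medical monitor adjudicates related events. Protocol 12 provides no clinical events committee. Any error therefore runs one way, towards a lower rate. It can also differ between the (up to three) sites according to how each reads the text.

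**Working it through.** The plan gives no expected rate, power or target for these endpoints, so there is no figure to reproduce. The check follows an event through the text and then sets the scale.

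**1. Path of an access or anesthesia complication after catheter insertion**

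| Step | Source | Effect |
|---|---|---|
| Is the procedure specific to the investigation? | Protocol 11.1.7, Appendix 17.5 | If no, it falls outside the stated procedure category |
| Would it have been applied without the device? | Same | If yes, *not related* |
| Is the event related? | Protocol 9, 9.8.5, 11.1, 11.1.1 | If no, it need not be captured |
| Is any CRF relatedness question answered YES? | SAP 7.7.2.2, 7.7.2.3 | Counted only if the event was captured |

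The SAP counts even *unlikely* as related. A firm *not related* is the rating that removes an event, and it is the rating that 11.1.7 assigns.

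**2. Whom each limit reaches**

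- *Absence of device.* Protocol 9 uses ENB to reach the nodule and place the catheter. If that is its only purpose, the ENB and its anesthesia would not have taken place without the device, so the sentence should not apply. It could apply where the bronchoscopy was going ahead for another reason. The protocol describes no such session.
- *Specific to the investigation.* The comparison here is with care outside the study. Sections 10.1.3 and 10.2 describe the imaging as routine and the ablation as obtainable without taking part. Read literally, this limit could reach an ordinary subject. The sentence that carries it refers to SAEs.

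**3. Effect of one lost subject**

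Change in rate = 100/N points: 100/30 = 3.3 and 100/20 = 5.0. N comes from the Synopsis: up to 30 subjects, with about 20 as the minimum.

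Exact 95% intervals, for scale only (SAP 7.7 plans an interval for the primary endpoint alone):

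| N | 1 subject recorded | 0 recorded |
|---|---|---|
| 30 | 3.3% (0.1% to 17.2%) | 0% (0% to 11.6%) |
| 20 | 5.0% (0.1% to 24.9%) | 0% (0% to 16.8%) |

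**4. How many events might be exposed**

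Protocol 4.1 cites a 3.1% pneumothorax rate for navigated bronchoscopy. Let m be the number of subjects whose access events a site would exclude. The documents do not give m, so a range is shown. Expected events = 0.031 × m; P(at least one) = 1 − 0.969^m.

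| m | Expected | P(at least one) |
|---|---|---|
| 0 | 0 | 0% |
| 1 | 0.03 | 3% |
| 3 | 0.09 | 9% |
| 20 (all, N=20) | 0.62 | 47% |
| 30 (all, N=30) | 0.93 | 61% |

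The last two rows are a ceiling for this one event type, assuming that every subject is affected. They are not a forecast. Some of these events would also precede catheter insertion and so fall outside collection in any case.

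**The case against.** The strongest reply is that the second limit asks about absence of the device, not of the study. Commercial availability, routine imaging and candidacy for ENB do not show that an ENB would have taken place without this catheter. That stands, and it removes the ordinary subject from that sentence. It does not answer the other limit, whose comparison is with care outside the study.

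A second reply is that the plan has safeguards.

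- Protocol 11.1.7 calls for clinical judgment, and unassessable cases default to *possible*.
- Section 9, headed as study procedures, describes ENB, access, CBCT and ablation.
- The CRF asks about each step separately.
- AEs are documented in source, with at least 80% source data verification (15.1).
- SAP 7.2 says that AEs for all enrolled subjects will be collected.

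These reduce the risk but do not close it. The default is for doubtful cases, not for an event that the text tells the site to call unrelated. The opening of Section 9 does not mention anesthesia. The SAP sentence does not override the protocol's related-only capture.

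A third reply concerns size. Protocol 6.2 reports 12 ablation-procedure AEs and no device-related AEs among 15 subjects in the sponsor's percutaneous study. A reader might infer that events of this kind would be lost here. The documents do not support that: those events came from the ablation itself, which would not occur without an ablation device. They show only that procedure attribution can carry most of the related-event signal.

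**Conclusion.** The wording of 11.1.7 and Appendix 17.5 does not match the two procedure-or-device endpoints, and related-only capture means that an excluded event may not be recoverable. The possible bias is downward and may vary by site. Each affected subject is worth 3.3 points at N=30 or 5 points at N=20. The number affected cannot be derived from the documents and may be zero.

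Two stronger readings do not hold. One is that both endpoints are certain to be biased: this depends on how sites read the text, and the typical catheter-only ENB should survive the absence-of-device sentence. The other is that the primary endpoint is undermined: it and the catheter-related SAE endpoint turn on relationship to the catheter and are less exposed.

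Severity: should-fix. The study is descriptive and unpowered and the endpoints are secondary, but its purpose is to characterize safety and the repair is small.

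**What to change.** In Protocol 11.1.7 and Appendix 17.5, add wording such as:

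> For the two endpoints on AEs and SAEs related to the procedure or study devices, neither the restriction to investigation-specific procedures nor the exclusion of procedures that would have been done without the device applies. Anesthesia, ENB navigation, access, procedural imaging, catheter placement and ablation in the index session are all study procedures, whether or not they would have been performed without the catheter.

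Cross-refer to this from SAP 7.7.2.2, 7.7.2.3 and 7.8.1.5, and send sites a short memo so that all apply the same rule.

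The cost is a small text change in the protocol, the reference list and the SAP, with no added visit, test or subject. The reported procedure-related rates may come out slightly higher.

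The change does not recover anesthesia or navigation events that occur before the catheter enters the EWC. Section 11.1 leaves those outside AE collection, and the report should say so when it presents these rates.
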